## 2.2 Research Overview

We will achieve our aims over two phases of the study.

**Phase I:** We will conduct focus groups with staff, including HIV C&T counselors, Health Educators, counselors and others. We will train a minimum of 2 Health Educators and 1 supervisor at each CBO. Once Health Educators demonstrate competence according to the MITI, we will move to Phase 2.

**Phase II:** We will recruit and enroll 260 MYMSM, aged 15-29, 130 per condition. Enrollment will be limited to HIV-negative YMSM who report recent substance use and either CAS or a positive STI result. Participants will be randomized to receive either the 4-session YMHP

intervention, or one session of eTAU. YMHP sessions will be audio-recorded for MITI fidelity coding, and counselors and supervisors will be given implementation support throughout. [TBD: Prior to implementation, immediately at the conclusion of the intervention delivery phase, and one year after, PRIDE will conduct interviews with counselors, supervisors, and CBO leaders to obtain information about the barriers to and facilitators of YMHP implementation and sustainment.]

### 3.0 STUDY POPULATION

#### 3.1 Inclusion and Exclusion Criteria

Patients who express interest in YMHP must demonstrate the following inclusion criteria to be enrolled in the study:

- HIV-negative test result from the past 90 days
- 15-29 years of age
- Currently identifies as male (regardless of birth sex)
- Sex with men in the past 90 days
- Self-report  $\geq$  3 days of substance use (including heavy drinking) in the past 90 days
- Self-report  $\geq$  1 episode of CAS in the past 90 days, *or* a positive STI test result in the past 90 days
- Living in NYC metropolitan area
- Able to communicate in English

Participants will be excluded from the study if they any indicate the following:

- $\geq$ 5 days of injection drug use (IDU) in the past 90 days
- Currently taking Truvada as pre-exposure prophylaxis (PrEP)
- Mental, physical or emotional capacity that does not permit them to complete the protocol as written.

We expect a study population that is close to 100% black and Hispanic, based on the client population at the partner CBO sites. However, we will not exclude young men of other ethnic or racial backgrounds from the study if they meet inclusion criteria. Given the racial and ethnic breakdown of YMSM clients at BOOM!Health and BAC, we estimate that 44% of our sample will identify as Black/African-American, 48% as Hispanic/Latino, and 8% as “other.”

#### 3.2 Recruitment and Screening

Recruitment and screening will be integrated into the HIV testing practices of both collaborating CBOs. BOOM!Health and BAC will continue to conduct HIV testing at their home offices and in the field as usual. YMSM that are tested and receive an HIV-negative result will be offered the opportunity to participate in YMHP. If interested, the HIV tester will ask the potential participant to complete a brief screener via an iPad. If eligible, the potential participant’s contact info will be

collected and passed on to the Research Coordinator who will contact them in order to schedule a baseline appointment.

CBO study personnel will also attempt to screen YMSM who have previously received an HIV-negative test result at BOOM!Health or BAC. To do so, CBO study personnel will reach out to YMSM who have received a recent negative HIV test result in the last 90 days. After giving an explanation of the YMHP study, the potential participant will be asked if he would like to answer the screener questions for the study over the phone. If he declines, the study personnel will thank him for his time and end the call. If they agree to answer the questions, the study personnel will deliver the study screener over the phone.

The study will be advertised in the form of flyers, brochures, and cards displayed in public areas of the BOOM!Health and BAC offices frequented by clients, plus their mobile testing units, alongside materials promoting the organizations' other services. These materials will be given to potential participants to encourage HIV testing as well as promote the YMHP study.

PRIDE will assist in identifying potentially eligible participants through its existing ongoing online recruitment efforts. PRIDE utilizes the Hunter College IRB-approved Online Master Screener (OMS) to preliminarily screen individuals who are interested in participating in PRIDE studies. When the OMS determines an individual to be preliminarily eligible for a study, they are asked to provide their contact information to PRIDE for follow-up. For this study, the OMS will be used to recruit, inform, and phone-screen potentially eligible YMSM to YMHP. PRIDE staff will conduct phone screens of potential participant identified by the OMS. If a YMSM screens preliminarily eligible for YMHP, they will be referred via email to BOOM!Health or BAC for free HIV testing to finalize eligibility. This referral email will contain additional information about the study. PRIDE will not provide the contact information collected through the OMS to the CBOs; however, the CBOs will be made aware that a potentially eligible YMSM has been screened for the study and added to the study database for follow up HIV testing.

We anticipate enrollment of 10 participants per site per month. We estimate that 80% of enrolled participants will be racial/ethnic minorities.

### 3.3 Contact Information

Once deemed eligible by the screener, participants will be routed to an online, Qualtrics version of the *Locator Form*. The information provided on the online *Locator Form* will be printed or pulled up by CBO staff for review in-person. The *Locator Form* asks participants to provide a street address, cell phone number, alternative phone number, and valid email address at which they can be reached. Participants will also be asked to provide valid phone numbers for two contacts who can be called in the event the participant cannot be reached by phone or email. Participants will be asked if voicemail messages can be left at the numbers provided. Site study staff will not leave messages unless expressly permitted to do so by the participant, as documented on this form. If permission is given to leave messages, site study staff will assure participants that messages left with a family member or friend will only ask the participant to

contact study staff and will not include any protected health information or information related to study participation. Participants will also be asked for permission to contact them via text message, and given the option to list any additional methods of contact including social media (Facebook, Twitter, Tumblr, Instagram). The *Locator Form* data will be maintained off-line in a password-protected file on a secure server, separate from all study records, with access limited to designated research personnel. A record that will link unique identification codes with names and contact information for participants will be accessible only to study staff and maintained off-line in a password-protected file on a secure server. Participants' names, addresses, email addresses, and social media information will not be collected in the survey, interview, or counseling sessions.

## 4.0 STUDY PROCEDURES

### 4.1 Enrollment Procedures

Participants are randomized to YMHP or eTAU after completing the baseline session, which includes the YMHP screener, completion of the Locator Form. After randomization, they are counted as officially enrolled in the study. Once enrolled, the participant should complete the session (YMHP #1 or eTAU, as assigned) immediately. The Research Coordinator will be responsible for tracking the visit as completed in REDCap. PRIDE will then verify that the baseline assessment was completed and follow up with the Research Coordinator if there are any data which need clarification.

#### 4.1.1 Informed Consent

Given that some of the participants will be under the age of 18, adequate provisions will be made for soliciting informed consent. At each site, the Research Coordinator will review the consent or assent forms to make a formal assessment of every youth's decision-making capacity to consent prior to signing, using a 2-step process. In the first step, the Research Coordinator will determine whether the person understands the goals by asking "Can you tell me what this study is about?" In the second step, s/he will ask questions designed to assess the potential participant's capacity to understand, appreciate, reason with, and express a choice about participation in our specific protocol. We will use a modified version of the widely used Evaluation to Sign Consent Form. Subjects will be asked to:

1. Name things they will be expected to do during the study,
2. Explain what they would do if they no longer wished to participate in the study,
3. Explain what they would do if they experienced distress during the study, and
4. Identify potential risks for participating in the study.

Participants will be enrolled only once they are able to provide clear and correct answers to each of these items, with assistance and clarification from the research staff member as needed. If the research staff member feels there is a question about the need for more formal assessment of the decisional capacity of a potential participant s/he will contact the Principal Investigator (PI) to make a decision about enrollment.

Consent will be discussed and documentation obtained in person at subjects' baseline visits prior to any data collection or other study procedures. The consent form (**Appendix A**) will be signed and dated by the individual obtaining the informed consent and by the participant at the beginning of the baseline assessment. A copy of the signed consent form will be given to the participant and the original(s) will be kept securely with each participant's research records. Signed consent forms will be filed and stored securely, and securely stored separately from other assessment materials because they contain the full names of participants.

The Research Coordinators will be trained on the protocol and the consent process, as well as receive Collaborative Institutional Training Initiative (CITI) training. CITI certificates will be submitted to the Hunter College IRB. The Research Coordinators will not engage in any research activity until they are registered as YMHP Research Staff with the Hunter College IRB and IRB approval is granted for their role on the research project. It is also possible for other site staff members (e.g., Health Educators) to be trained and cleared to obtain consent.

Sites will use a local authorization to release protected health information (PHI) to PRIDE as per their institutional policy. Participants will also sign a research authorization for use and disclosure of PHI as required by the IRB.

#### **4.1.2 CASI**

After obtaining informed consent, participants will complete a confidential computer-based survey (CASI) at the CBO site that will ask about their substance use, sexual behavior, and general thoughts and feelings. CBO study staff will administer the baseline CASI survey on a study-designated iPad or computer and ensure the participant can complete the survey in a quiet place. The participant will be able to reach the assessor if they have any questions or encounter errors completing the survey, but the assessor will not be in the room so that the participant completes the CASI in private. The baseline CASI will take about 45 minutes to complete.

Participants who screen ineligible based upon CASI responses will be dropped from the study and all relevant databases. They will be given a \$25 gift card for completing the CASI. This was changed in August, 2019 because too many participants were incorrectly answering study eligibility questions on the BL CASI. After that point, Study eligibility was determined at screening.

#### **4.1.3 STI Testing**

If eligible to continue based on the CASI, participants will proceed to STI testing, which will consist of a urine sample, an anal self-swab of rectal mucosa, and a syphilis test (type dependent on participant's history of syphilis). The syphilis tests used in this study do *not* require a phlebotomist. The STI testing process will take about 15 minutes.

*All participants will have already taken an HIV test in the last 90 days, with a negative test result. This is the baseline HIV status. The next HIV test will occur as part of the 3 Month Follow Up Visit.*

See Section 4.6 for specimen collection and STI test result reporting procedures.

#### 4.1.4 Randomization

Participants will be randomized at the end of their baseline assessment into one of two intervention conditions: 1) delivery of the 4-session YMHP intervention or 2) delivery of a single eTAU session. Each participant's condition will be tracked in the REDcap database maintained by the Research Coordinator.

To assign condition, the study employs a stratified block randomization procedure with strata for interventionist and substance use. Interventionists are crossed by condition rather than nested, allowing for a more statistically powerful design. The assigned interventionist will be used for these particular strata. The substance use strata will randomize based on whether the participant used only marijuana in the past 3 months versus use of another drug in the past 3 months. After a participant completes the CASI, the assessor will open the randomizer in Qualtrics. The assessor will enter the participant's ID, the assigned interventionist, and select either "marijuana-only" or "other substance use" into the randomizer. The block randomization procedure will select the condition.

### 4.2 Schedule of Assessments

**Baseline (first) visit:** After providing informed consent, completing the CASI, and collecting specimens for STI testing, participants will complete their first session of YMHP, or their first and only session of eTAU, depending on their randomization. If randomized to receive the YMHP intervention, this first session will take 40-50 minutes to complete, focusing on either sexual risk or substance use, and will be audio recorded. If randomized to receive eTAU, the session will take 30-45 minutes, and will also be audio recorded. After this first visit, there are no additional treatment sessions as part of eTAU.

**Additional YMHP sessions:** Participants randomized to YMHP will have the first YMHP session immediately after completion of the baseline assessment, and then they will return to the CBO to receive the remaining 3 intervention sessions, focused on sexual risk and substance use. Intervention sessions should occur approximately once per week for a total of four weeks, inclusive of the baseline visit. There is a 12 week window for intervention completion, i.e. all 4 YMHP sessions must be completed within 12 weeks of the baseline assessment. Thus, if participants need to miss a week periodically, for any reason, they should have ample time to complete the four sessions during the 12 week window.

**Immediate post-test assessment:** After completing all 4 YMHP sessions, or the single eTAU session, participants will be scheduled to complete an immediate post-test assessment. This assessment will occur about 3 months after their baseline visit (i.e. the first follow-up assessment

post-baseline). During this assessment participants will complete a confidential computer-based survey about their substance use, sexual behavior and general thoughts and feelings. In addition to assessing the primary outcomes of the intervention, participants will also respond to process measures. Specifically, participants will be asked to provide an evaluation of their health educator, as well as the health care climate of the YMHP intervention. This survey can be completed at the clinic or through a survey link, which will be sent to participants electronically, and will take about 45 minutes to complete.

**Follow-up assessments:** There will be four additional follow-up assessments for participants to complete. These follow-up assessments will occur in three-month intervals until 12 months after their post-intervention assessment (i.e. 3 months, 6 months, 9 months, 12, and 15 months post BL).

The 3 month and 9 month follow-up assessments include completing a confidential computer-based survey (CASI) on an iPad and require confidential HIV and STI testing. The HIV and STI testing should be performed at the CBO clinic but other options are available such as getting tests performed at an outside lab (e.g. Quest Diagnostics) or by using a self-test kit which will be mailed to the participant if they choose. If participants do not complete the 3 month or 9 month HIV and STI testing they will be asked to complete these tests at their next assessment.

The 6 month and 12 month assessments do not require HIV and STI testing (unless testing is missed at a previous visit) so these assessments can be completed remotely. Participants can use an electronic link provided to them or they can complete the CASI at the CBO site if they choose. The CASI assessment will be similar to the one administered at baseline and will take about 45 minutes for the participant to complete.

The immediate post-test and follow-up assessments will be administered by a Research Coordinator or a trained and cleared Health Educator. No Health Educators may administer an assessment to a participant to whom they administered eTAU or YMHP sessions.

**Optional Qualitative Interview:** In an effort to understand barriers and facilitators to YMHP program participation, we are adding an optional qualitative interview with study participants post intervention. It can be completed at the immediate post or at any time after the intervention window has closed (3 months post BL). The qualitative interview will be conducted over the phone between a PRIDE Staff member and the participant and should take approximately 30 minutes.

	Screening	Baseline	IP	3M FU	6M FU	9M FU	12M FU
Informed Consent		X				X	
CASI		X	X	X	X	X	X
HIV Testing	X			X		X	
STI Testing		X		X		X	
Randomization		X					

Refer to “Study Design” for a visual representation of the schedule of assessments.

#### 4.3 Managing and Tracking Study Visits

All participant tracking and retention activities are managed at the two CBO sites, since participants are mainly recruited at these sites. There are two different types of databases (Contact and Tracking) housed on REDCap, an online application, used to log staff contact with participants and participant progress in the study. This system allows both site Research Coordinators and PRIDE to monitor the completion of study visits and surveys, and generate reports on enrollment and retention as needed. The Research Coordinators are expected to track all completed study components in REDCap immediately after completing an assessment or upon receiving of e-mail notification of session completion no later than the end of the business day.

[figure not shown]
**Intervention Visits:** Intervention tracking includes database entries of all YMHP sessions completed by the participants. Intervention sessions will be largely managed by the Health Educators with their individual study participants. The tracking mainly involves four components – delivery of the YMHP session, completion of the *Clinical Session Note Form*, uploading audio files, and sending an e-mail notification to the study team. Using the central study e-mail account, Health Educators will notify their CBO’s Research Coordinator and PRIDE of whether sessions were completed for tracking purposes, submit electronic *Clinical Session Form*, and upload audio files to the study Dropbox folder as per study procedures. PRIDE will notify the Health Educators to acknowledge receipt of the *Clinical Session Form* or to remind them to complete the form. The Health Educators will be responsible for scheduling the YMHP sessions 2-4 for participants randomized into YMHP.

Intervention visits include all YMHP sessions between enrolled study participants and MI-trained Health Educators. Intervention visits will be largely managed by the Health Educators with their individual study participants. Health Educators will notify site study staff of whether

visits were completed for tracking purposes, provide receipts for session compensation to site study staff, and upload audio files to Dropbox as per study procedures. The 1st YMHP appointment or one-time eTAU occurs directly after the baseline appointment.

**Assessment Tracking:** Assessment tracking includes entries of the baseline visit, the immediate post-test assessment, and all four follow-up assessments in REDCap. All participants, regardless of randomized condition, are expected to complete the six assessments as part of full participation in the study.

For each assessment, the participant will complete the CASI using an iPad (if completed in person at the clinic) or using a phone, tablet, or other computer device (for assessments that can be completed at home). Research Coordinators will schedule participants for in-person assessments during times that they will be available. Research Coordinators will also ensure that there is available space at clinic sites to conduct these assessments. Research Coordinators are expected to keep in touch with participants and remind them of the upcoming visit and reschedule if/when needed. A reminder call should be made one business day before a participant is due to come in for a study visit (i.e. the Friday before a Monday visit). Participants who wish to forego an in-person visit to the clinic site have the option of completing follow-up assessments online (i.e. without coming to the clinic) for visits which do not require HIV and STI testing (6-Month Follow-Up and 12-Month Follow-Up). These assessments consist only of an online CASI. Participants may contact Research Coordinators by phone or email about any questions or concerns that arise while completing these surveys. The *Study Data Flow* is presented below.

#### 4.4 Retention and Follow Up

We estimate that retention for the IP and the 3, 6, 9, and 12-month Follow Up assessments will be about 97%, 94%, 91%, 88%, and 85%, respectively, based on our prior work on YMHP. Through the REDCap Tracking Database, PRIDE YMHP staff will generate weekly reports listing all participants who are due for follow-up assessments. PRIDE will provide extensive training to the CBO Research Coordinators on retention efforts.

**Session Retention:** For patients who are actively taking part in the YMHP intervention and working with Health Educators, site study staff will not add an additional level of outreach to the procedures. Health Educators will be instructed to adhere to the already-present procedures of the CBO for contacting and re-scheduling patients. Research Coordinators should prioritize the completion of intervention sessions before the first follow-up assessment, and should not schedule this follow-up less than 12 weeks after baseline if a participant is available to complete any additional sessions first.

**Assessment Retention:** A target date for completing each follow-up will be established at every 12-week point from the baseline. Research Coordinators should aim to schedule and complete these follow-ups as close as possible to each target date. Given that this is an effectiveness trial in a real-world setting, assessment windows are liberal. To keep track of longitudinal data collection dates, assessment windows will be programmed to 30 days prior and after the target as “in window.” If Research Coordinators attempt to assess a participant 60 or more days before or after the established target date, then they should contact PRIDE to authorize the assessment prior to compensating the participant.

Research Coordinators are to maintain strong and consistent relationships with study participants, and should contact study participants by phone at least once per month. During this phone outreach, Research Coordinators can verify existing contact information and inquire as to whether the participant foresees any potential changes in the near future. Research Coordinators should take note of participants who are less stable in terms of housing/phone numbers, and devote outreach efforts toward these participants strategically. Retention success/challenges will be based on outreach and assessment reporting from Research Coordinators at each site to PRIDE via Qualtrics. PRIDE will generate weekly reports using REDCap and distribute them to staff at each site. PRIDE and the Research Coordinators will meet regularly to discuss recruitment and retention efforts, based on these reports and any other relevant feedback.

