Outcome analyses were conducted using piece-wise latent growth curve (LGC) models following procedures outlined by Chou et al., (Chou et al., 2010) and used previously in similar studies (Flora, 2008; Kohli et al., 2013; Li et al., 2001; Naar-King et al., 2009; Naar et al., 2020). Growth trajectories over-time following the delivery of an intervention may be characterized by a large initial response followed by a more sustained trajectory with a less dramatic slope. Piece-wise LGC models quantify this kind of trajectory through the use of two slopes. Slope 1 quantifies the change from baseline to the immediate post-test (3-month follow-up). Meanwhile, Slope 2 quantifies the trajectory over the post-intervention follow-up period.

All primary (marijuana use, other illicit drug use, and CAS with male partners) and secondary (alcohol use) outcomes were modeled as negative binomial distributions. All models were estimated using full-information maximum likelihood estimation in MPlus Version 8.0. This permitted the retention of all randomized cases consistent with a true intent to treat paradigm. Many commonly used indices of model fit are not available for growth models with count-distributed outcomes (i.e., root-mean square error of approximation (RMSEA)  $\leq 0.05$ , Tucker-Lewis fit index (TLI)  $> 0.95$ , and comparative fit index (CFI)  $> 0.95$ ). Model fit was therefore

evaluated using a robust log-likelihood  $\chi^2$  test (Satorra & Bentler, 2001) comparing the log-likelihood of the specified model to a null-model – in which all structural coefficients associated with the regression of latent growth factors on condition and site were constrained to be zero.

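### The hold on the first follow-up can bind only in YMHP, so the immediate post-test can fall earlier on average in eTAU, and Slope 1 is defined by wave with no stated use of actual dates

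*Combined protocol and SAP*

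**What the plan says.** **The hold.** The session-retention paragraph of section 4.4 opens "For patients who are actively taking part in the YMHP intervention and working with Health Educators". It tells coordinators to put completing sessions ahead of the first follow-up assessment, and says they "should not schedule this follow-up less than 12 weeks after baseline if a participant is available to complete any additional sessions first". Section 4.2 identifies the immediate post-test as the first follow-up after baseline.

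**eTAU.** Section 4.2 says that after the baseline visit "there are no additional treatment sessions as part of eTAU".

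**Target and window.** The assessment-retention paragraph of 4.4 makes no distinction by arm: "A target date for completing each follow-up will be established at every 12-week point from the baseline". It adds: "Research Coordinators should aim to schedule and complete these follow-ups as close as possible to each target date". Thirty days either side of the target counts as in window. Prior authorisation is needed only when a coordinator attempts to "assess a participant 60 or more days before or after the established target date".

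**Model.** Section 6.2 (Phase 2, statistical analysis) says: "Slope 1 quantifies the change from baseline to the immediate post-test (3-month follow-up". It does not say whether time scores are nominal or actual, and it plans no analysis of assessment timing. The primary and secondary outcomes in 6.2 all cover the past 30 days.

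**The concern.** The hold depends on sessions still being available. That condition can be met in YMHP and never in eTAU. For a YMHP participant with sessions left, the early half of the window is closed; for an eTAU participant it stays open. Section 4.2 also lets the immediate post-test be done through a survey link, which makes an early visit easy.

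Timing matters because of the short recall period. A visit on day 54 measures roughly days 24 to 54, and a visit on day 84 measures days 54 to 84. Both are in window, yet the periods do not overlap. Enrolment requires recent substance use together with recent condomless anal sex or a positive STI test, so a fall in both arms through regression to the mean is plausible. If one arm is measured later along that fall and the model places both arms at the same wave, part of the common change is credited to treatment. Randomisation does not protect against this, because the scheduling rule acts after assignment. If behaviour falls over time, the error favours YMHP, and it sits in Slope 1, the term meant to capture the initial response.

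**Working it through.** The plan gives no figure for assessment timing, so there is nothing to reproduce. The check is window arithmetic followed by a bound.

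**1. Windows (section 4.4).**
- Target: 12 × 7 = day 84, both arms.
- In window: 84 − 30 = day 54 to 84 + 30 = day 114.
- Earliest day without authorisation: 84 − 59 = day 25.
- YMHP participant held by the rule: days 84 to 114 in window.
- eTAU participant, or YMHP participant who has finished: days 54 to 114 in window.

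**2. Who is held (section 4.2).** Sessions run about weekly over four weeks, so participants on schedule finish around days 21 to 28. That is before day 54, and the rule does not touch them. Sessions must end within 12 weeks of baseline, so the rule never asks for a visit later than the common target.

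**3. Mean shift per held participant.** Assume visits otherwise spread evenly over days 54 to 114, with mean day 84.
- Early visits simply move to day 84: half of the visits move by 15 days on average, so the shift is 0.5 × 15 = 7.5 days.
- Held visits spread evenly over days 84 to 114, with mean day 99: the shift is 99 − 84 = 15 days.

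**4. Spurious ratio.** Assume no treatment effect and a common proportional decline x from baseline to day 84, linear on the log scale. With a share f of YMHP held, the arm gap is d = f × shift, and the spurious YMHP:eTAU rate ratio is (1 − x)^(d/84). For x = 30%:

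| Share of YMHP held | Gap, moved to day 84 | Ratio | Gap, spread over days 84–114 | Ratio |
|---|---|---|---|---|
| 10% | 0.75 days | 0.997 | 1.5 days | 0.994 |
| 25% | 1.88 days | 0.992 | 3.75 days | 0.984 |
| 50% | 3.75 days | 0.984 | 7.5 days | 0.969 |

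For example, 0.70^(7.5/84) = exp(−0.357 × 0.0893) = 0.969. Across the table the spurious reduction runs from about 0.3% to about 3%.

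**5. Other declines.** Over the same table, x = 10% gives ratios from 0.999 to 0.991, and x = 50% gives 0.994 to 0.940.

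**6. Visits on target.** If coordinators meet day 84 in both arms, d = 0 and the ratio is 1.

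**The case against.** The strongest reply is that the documents prescribe the same timing in both arms. There is one target, an instruction to keep close to it, and section 4.2 and the abstract both place the immediate post-test about 3 months after baseline whatever the arm. The hold only points YMHP participants back to that target. This stands. A reader might infer that the post-test *is* timed differently by arm. The text supports only that it *can* be, and only if visits are booked early where the hold does not apply.

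Three further inferences also go too far:

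- **A 30-day gap between arm means.** Within the window this needs something like every eTAU visit on day 54 and every YMHP visit on day 84. The ratio would then be 0.70^(30/84) = 0.880, but nothing in the documents makes that realistic. Day 25 is likewise where the authorisation threshold begins, the same for both arms, and not a planned visit day.
- **A comparison with the 24% and 18% in section 1.4.** Those are reductions in the likelihood of behaviours in an earlier trial against content-matched education. They are not Slope 1 rate ratios for counts.
- **Fixed time scores as a stated specification.** Section 6.2 describes Slope 1 in words. Fixed waves are a fair reading of its silence about dates, no more.

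The log-linear decline is also an assumption. If most of the fall has happened by day 54, the effect is smaller than shown.

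The reply does not remove the rule itself, which closes the early side of the window in one arm only. Nor does it supply an analysis that would show whether this mattered.

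**Conclusion.** The point holds as a possible small bias, not an established one. The earliest-date restriction is written so that it can operate only in YMHP, and only for participants with sessions outstanding, while the analysis text names no safeguard for differences in timing. The 0.3% to 3% range rests on the share held, the spread of visits and the common decline, none of which the documents give. The direction favours YMHP if behaviour falls over time and would reverse if it rose. The trial's own visit dates can settle whether the gap is zero or material, so the plan should use them.

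**What to change.** **Section 4.4.** Apply the same earliest-date rule for the first follow-up to both arms, regardless of sessions remaining. This costs one sentence; the small downside is that some eTAU visits are held slightly later.

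**Section 6.2.** Report the distribution of days from baseline to the immediate post-test by arm. State whether the primary piecewise model uses nominal or actual times, and add a sensitivity analysis with each participant's actual assessment times as time scores. The dates should already exist: section 4.3 has completed assessments tracked in REDCap, and 4.4 says the windows are there to keep track of collection dates. The cost is one table and one further model run per outcome.

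The analysis plan was updated in October 2021 and section 6.2 describes the outcome analyses in the past tense, so visits may be over. In that case the change to 4.4 no longer has any effect, and the changes to 6.2 alone apply.
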